- e) Vulnerable Subjects:** Individuals who are 60 years of age and older with social risk factors for poor mental and physical health outcomes will be included. The results of this study will inform future research and clinical interventions aimed at improving mental health treatment for older adults.

III. METHODS AND PROCEDURES

- a) Design:** The design is a randomized controlled trial. Community dwelling older adults (n=300) will be randomly assigned to either the volunteering condition (volunteering) or self-guided life review condition (life-review). Those subjects assigned to volunteering will volunteer through Senior Corps by participating in social volunteer assignments offered by RSVP as part of their standard process for placing volunteers. Those subjects assigned to life review will complete a series of self-guided (with minimal email support) life review writing experiences over 12 months. All subjects will receive repeated assessments over the course of the study (baseline, 3, 6, 9, 12 months). The 3 and 9 month assessments will be online/mail at home or in-person.
- b) Intervention Setting:** Those randomly assigned to the volunteering condition will receive the intervention at Lifespan as well as Lifespan volunteer placements in the community per standard RSVP policy and procedures. Those randomly assigned to the life review condition will receive the intervention via the phone (for training) and their homes via email/mail.
- c) Recruitment Setting:** Subjects will be recruited from the Greater Rochester Practice Based Research Network. The GR-PBRN is a network of primary care practices coordinated by the University of Rochester's Clinical Translational Science Institute to provide access to subjects and community-based practices for research. The 31 family medicine and internal medicine practices that constitute the network care for approximately 217,000 patients, of which approximately 50,000 are over age 60 and therefore eligible for initial screening for the study.

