(i) **Overview:** The purpose of the Data and Safety Monitoring Plan (DSMP) is to specify the procedures and rationales of the current study to ensure the safety of participants and the validity and integrity of the data. This specifies who will look at the data and review any adverse events, how often, and what they are authorized to do. The use of Data and Safety Monitoring Boards (DSMBs) may be indicated if the studies have multiple clinical sites, are blinded (masked), and/or employ particularly high-risk interventions or vulnerable populations. This study on the other hand will be conducted utilizing a low risk intervention in a population of older adults residing independently in the community. Therefore, we have chosen to include a *modified DSMB* that, while constituted by individuals connected to the study, will systematize monitoring safety issues throughout its duration.

(ii) **DSMB Membership:** [name] will chair the DSMB. [name] is Professor of Psychiatry at URMC and an expert in research and clinical care of older adults. Other members will include [name] [name]., [name]., and [name]. [name] is the principal investigator of the project and [name] is a Co-Investigator and geriatric psychiatrist. [name] is the outside member of the DSMB and is a clinical geropsychologist.

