(iv) **Meeting Schedule:** At a minimum, the DSMB will convene on an annual basis. DSMB conferences will be assembled in-person, and conducted in accordance with federal and state health privacy

legislation and relevant standards. The Chair and the P.I. will determine meeting logistics based upon urgency and the availability of DSMB members.

(v) Adverse Events (AEs) and Serious Adverse Events (SAEs).

We will abide by the rules governing reporting of adverse events as defined in NIH Policy on Data and Safety Monitoring in Clinical Trials (September 2002, revised 2007). Any event will be reported to the RSRB if it is “serious,” “unexpected,” and “related.”

Reportable Events: Definition of terms

- “Serious” means any event that causes a prolonged or permanent harm that is psychological, social, legal or financial. Examples most pertinent to this study include a subject’s death from any cause; a suicide attempt or hospitalization due to depression.
- “Unexpected” means that the event was unforeseen and has not been previously encountered, known, or recognized and was not identified in nature, severity, or degree of incidence in the protocol, supporting documentation, the informed consent document, or the RSRB application.
- “Related to the study” means that there is some aspect of the study (e.g., a research procedure, existence of a laptop database, etc.) that is directly related to the event. An example pertinent to this study is breach of confidentiality by which private information about the subject was made known to other community members. Events for which the relationship to the study cannot be clearly determined based on review of all available data will be classified as “possibly related to the study” and reported according to the same guidelines as for related events.
- “Event” is an incident, experience, or outcome that occurs to a subject participating in an RSRB-approved research study.

The following rules describe the procedures for adverse events that will guide us:

- AEs are reported to the sponsor, regardless of whether they are considered study related. They may include hospitalization or death.
- The date and time of onset and outcome, course, intensity, action taken, and causality to study treatment will be assessed.

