- The Principal Investigator has the final decision regarding what is to be reported on the adverse event form, and has the option to reclassify an AE as a serious adverse event (SAE). In general, a serious adverse event (SAE) is an event where a relationship to the research study cannot be ruled out and the event is life threatening/results in death OR disabling/incapacitating OR requires or prolongs hospitalization OR involves an overdose OR was otherwise unanticipated, related to the study procedures or could lead to one of the other serious event conditions.
- In case of an SAE: The date and time of onset and outcome, course, intensity, action taken, and relationship to study treatment will be assessed. SAEs will be reported to the CDC, DSMB, and the RSRB within 24 hours. A written report will be forwarded to NIH, DSMB and the RSRB within 5 working days of the investigator’s discovery of the event.

i) Data Storage & Confidentiality:

Electronic data will be collected in a password protected, secure web-based application called REDCap (Research Electronic Data Capture). This web-based data entry system replaces the current process of collecting data on paper copies and entering the data afterwards via a system residing on a local computer. The electronic data capture system provides a secure, HIPAA-compliant web-based application that is flexible enough to be used for a variety of types of research, provides an intuitive interface for users to enter data and has real time validation rules (with automated data type and range checks) at the time of entry.

REDCap servers are housed in a local data center at the University of Rochester and all web-based information transmission is encrypted. REDCap was developed in a manner consistent with HIPAA security requirements and is recommended to University of Rochester researchers by the URMC

Research Privacy Officer and Office for Human Subject Protection. A laptop or iPads will be used to collect the encrypted data on REDCap.

No protected health information will be stored on portable media, including laptop computers or removable hard drives. The data (including names and all identifiable information) will be encrypted using SSL. Only authorized study personnel and regulatory personnel (e.g. auditors) will be allowed access to data. All access to the database will be controlled by passwords with varying levels of security and access. The iPads or laptop will be used by the coordinator and subject.

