Due to Covid-19 restrictions, all study visits are remote. These changes will remain in effect until URMC/NIH guidance changes regarding research and our high risk population (people over the age of 60). We have reassessed safety procedures and obtained DSMP guidance and will allow volunteer activities that RSVP has approved for volunteering. These agencies will have a documented safety plan and will be reviewed by members of our DSMP Committee. Any subject wishing to participate in at home volunteer activities may still continue to do so. Any additional changes will be reviewed by our DSMP committee and discussed with program officer before we will revert to our original protocol and resume all in-person activities.

Study visits – Baseline, 6 months and 12 months will be conducted via phone or zoom and online. 3 and 9 month surveys will remain remote either online or by phone. If a subject is unable or unwilling to use zoom, the visits will be done by phone with self-administered studies sent by e-mail.

Consent – Consent will be done at the baseline visit over the phone or through zoom. At the screening call, the study coordinator will ask the subject whether they want to use phone or zoom. E-consent will be done through the REDCap module. The study team will obtain verbal permission to send the eConsent via email. Verbal permission will state: “Because URMC can’t control the security of email messages once we send them, we need your permission to email you. Do you want to receive the link to the eConsent via email?” The permission will be documented. The email will not include PHI.

To verify the subject’s identity - the study team will add security questions to answer at the time of accessing the survey/eConsent. These questions will be pre-established security questions such as “What is your favorite color?” or “What is the name of the street you grew up on?” that are included on the signature page of the eConsent. The responses will be agreed upon by both the study team and the subject during the screening call. The answers will be saved in the subject record for verification later.

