Strategy 11: We are adding recruitment strategies via our geriatric medicine practices at UR Medicine. The UR Medicine Geriatrics Group will place our informational brochures in waiting rooms and patient exam rooms. UR Medicine Home Care (URMHC) will share brochures with patients who receive their services. In addition we may contact potentially eligible URMHC clients who have indicated that they are interested in participating in research when they complete the consent process via URMHC. In 2021, URMHC developed and implemented a process for existing URMHC patients to indicate willingness to be contacted about participation in research studies. These procedures are part of a clinical workflow conducted by clinicians; responses are contained in a clinical database. Using this process, URMHC patients, while receiving HHC visits, will be asked if they agree to be contacted by URMC researchers for future research participation, knowing that each study will be introduced and consent will be sought individually. If the patient agrees to be contacted by URMC research about future

research opportunities, he/she will choose “yes”, sign, and indicate their preferred contact method (i.e., phone, email, or mail). This information has been incorporated electronically, along with the signature, in the URMHC electronic health records. Upon IRB approval, URMHC will provide a list of URMHC patients who have consented for future research contacts at the time for their initial HHC visits, along with their contact information. Study staff will contact those patients and explain the study per the verbal script. If interested, the screening questions will be completed by phone.

References

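### The investigator decides what goes on the adverse event form and sits on the board that monitors those reports; nobody else is described as checking what is left off or not classed as serious

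*Combined protocol and SAP*

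**What the plan says.** Section III.h(v) begins its AE rules broadly: "AEs are reported to the sponsor, regardless of whether they are considered study related". A later bullet in the same list says "The Principal Investigator has the final decision regarding what is to be reported on the adverse event form", and adds that the investigator "has the option to reclassify an AE as a serious adverse event (SAE"). That bullet then gives a general description of an SAE. It requires that a relationship to the study cannot be ruled out, together with one of several outcomes such as death, incapacity or hospitalization. The definitions earlier in III.h(v) differ: under serious events they list a subject's death whatever its cause.

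Section III.h(iii) has the DSMB monitor AE reports for nature, frequency and severity, and keeps it informed of severe events as they occur. Section III.h(i) calls this a modified board made up of people connected to the study. Section III.h(ii) describes a chair, a member who "is the principal investigator of the project", a co-investigator, and one member identified as outside. No recusal rule is given.

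The board's rationale, in III.h(i), is that a DSMB may be indicated for vulnerable populations among other conditions, whereas this trial tests a "low risk intervention in a population of older adults residing independently in the community".

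**The concern.** The person who decides what is recorded also helps judge the record. No criteria limit that decision, and the plan does not say that an event meeting the SAE description must be treated as one. If an event is left off the form, or stays an ordinary AE although it fits the SAE description, no later step in the plan is designed to find it.

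This matters even in a low-risk trial. Section III.h(v) names suicide attempt and hospitalization for depression as pertinent serious events, and IV.2 accepts that both interventions may cause distress and that negative outcomes cannot be excluded. The board can judge whether event frequencies match expectation only if the reports reaching it are complete.

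**Working it through.** The plan gives no figure to reproduce, and no power or effect-size input bears on the point. The check sets the passages side by side.

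**1. The recording rule.** The sponsor rule removes relatedness as a reason for not reporting. The later bullet gives one person the final say on the form's content and names no ground on which an event may or may not be left out. The two sentences can be read together, but nothing in the second ties the investigator's decision to the first.

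**2. The classification rule.** The stated power runs from AE to SAE only. It is worded as an option, and the SAE description beside it is introduced as a general one. The text does not say that classification follows automatically once the description is met. The description also depends on relatedness not being ruled out, and no person independent of the investigator is assigned that judgement.

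**3. The reviewing body.** Members described in III.h(ii): chair + principal investigator + co-investigator + outside member = 4. Study investigators: at least 2 of 4. Described as outside: 1 of 4. The chair's relation to the study team is not stated, and names are removed, so it cannot be determined.

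**4. What starts each review route.**

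| Route | Where | What it acts on |
|---|---|---|
| Sponsor | III.h(v) | AEs that are reported |
| DSMB monitoring | III.h(iii) | AE reports, and severe events made known to it |
| CDC, DSMB and RSRB within 24 hours | III.h(v) | events classed as SAEs |
| NIH, DSMB and RSRB in writing within 5 working days | III.h(v) | events classed as SAEs |
| RSRB reportable events | III.h(v) | events judged serious, unexpected and related (or possibly related) |

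Every route starts from an event already recorded or classified. None is described as comparing the forms with interview records, Lifespan reports or any other source. This step assumes that the AE form feeds the reports; the plan names no other AE record.

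**5. Internal consistency.** A death judged unrelated is serious under the definitions in III.h(v) but falls outside the SAE description a few lines later. Separately, III.h(i) contrasts this trial with those in vulnerable populations, while II.e, headed as a section on vulnerable subjects, says: "Individuals who are 60 years of age and older with social risk factors for poor mental and physical health outcomes will be included". That describes the trial's own population.

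**The case against.** The strongest reply is that review outside the investigator does exist. There is an outside board member, AEs go to the sponsor regardless of relatedness, SAEs reach the RSRB within 24 hours and NIH in writing within 5 working days, and events of uncertain relatedness are reported as possibly related. This stands. A reader might infer that harms receive no independent review, and the documents do not support that. What remains is narrower: these routes depend on what is recorded and classified first.

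Second, the reclassification wording can be read as letting the investigator escalate beyond the definition. That reading is fair. A reader might infer a power to downgrade, but none is written. The exposure is omission or failure to upgrade.

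Third, a lighter board is openly disclosed for a trial that IV.1 rates as minimal risk. That also stands. A reader might infer that the low-risk premise is contradicted because the addendum speaks of "our high risk population (people over the age of 60") and Strategy 11 recruits through home care. The first phrase explains remote visits under Covid-19 restrictions and does not rate the intervention. The second is a recruitment channel whose patients must still meet the eligibility criteria. Neither contradicts III.h(i). Only the heading and text of II.e are in tension with it, and III.h(i) says only that a DSMB may be indicated in such populations.

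Finally, III.g plans no between-arm comparison of AEs, so no planned estimate would be biased. That is correct, and the point is not made on that ground.

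**Conclusion.** The point holds as a gap in safety recording and oversight. The investigator has the final decision on AE form content, shares in the board's review of AE reports, and is subject to no described check on events omitted or not classed as SAEs. At least two of the four described board members are study investigators, and one is described as outside. The number of events that could be affected cannot be estimated, because the documents give no AE rates.

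The conclusion rests on the text as written and on the assumption that the AE form is the source for the later reports. It does not depend on whether the investigator is masked, on the chair's independence, or on any suggestion that events would be withheld. The mismatch between III.h(i) and II.e is secondary: correcting it alone would change nothing the trial does. The change should be made because it concerns participant safety and costs little, but it does not threaten the primary analysis.

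**What to change.** 1. Reword the bullet in III.h(v): every AE the team learns of is entered on the form; the investigator may add an opinion on causality but may not omit an event; an event that meets the SAE definition is an SAE without discretion. This brings the bullet into line with the sponsor-reporting rule above it. Reconcile the SAE description with the earlier listing of death from any cause, so that one definition governs.
2. Add to III.h(ii) or (iii): the principal investigator and co-investigator on the board abstain from judging SAE status and relatedness, which fall to the members who are not study investigators. On the described membership that leaves 4 − 2 = 2 people, or 1 if the chair also belongs to the study team. The plan should state which applies.
3. As a secondary edit, reconcile the contrast with vulnerable populations in III.h(i) with II.e.

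The cost is protocol wording, slightly more AE entries, and fewer members deciding on each event. The edits need no new assessments and no change to the analysis.

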Due to Covid-19 restrictions, all study visits are remote. These changes will remain in effect until URMC/NIH guidance changes regarding research and our high risk population (people over the age of 60). We have reassessed safety procedures and obtained DSMP guidance and will allow volunteer activities that RSVP has approved for volunteering. These agencies will have a documented safety plan and will be reviewed by members of our DSMP Committee. Any subject wishing to participate in at home volunteer activities may still continue to do so. Any additional changes will be reviewed by our DSMP committee and discussed with program officer before we will revert to our original protocol and resume all in-person activities.

Study visits – Baseline, 6 months and 12 months will be conducted via phone or zoom and online. 3 and 9 month surveys will remain remote either online or by phone. If a subject is unable or unwilling to use zoom, the visits will be done by phone with self-administered studies sent by e-mail.

Consent – Consent will be done at the baseline visit over the phone or through zoom. At the screening call, the study coordinator will ask the subject whether they want to use phone or zoom. E-consent will be done through the REDCap module. The study team will obtain verbal permission to send the eConsent via email. Verbal permission will state: “Because URMC can’t control the security of email messages once we send them, we need your permission to email you. Do you want to receive the link to the eConsent via email?” The permission will be documented. The email will not include PHI.

To verify the subject’s identity - the study team will add security questions to answer at the time of accessing the survey/eConsent. These questions will be pre-established security questions such as “What is your favorite color?” or “What is the name of the street you grew up on?” that are included on the signature page of the eConsent. The responses will be agreed upon by both the study team and the subject during the screening call. The answers will be saved in the subject record for verification later.

The consent process will be the same as in-person. The consent form will be read aloud to subjects, who will be encouraged to ask questions throughout the process. At the conclusion of the consent process and prior to requesting that they sign the form, all subjects are asked capacity questions prior to signing. Subjects will certify that the information in the document is correct (which includes their name), and that electronically signing is the equivalent of signing a physical document. Subjects will sign using finger, mouse or stylus. The study coordinator will sign electronically as well. Consents will be stored within REDCap, and a copy will be e-mailed to the subject.

Intervention – Volunteering will remain through RSVP and may include both in the community and at home volunteer activities. Placements in the community are reviewed by RSVP and will have a documented safety plan.

Measures: The only measure that will need some adjustment will be the MOCA. If a subject cannot use zoom, a few of the visual questions would not be able to be performed. MOCA

without the visual elements is considered the Blind version of the test and can be used with a modified cutoff score given that the maximum total score for the Blind version is 22 and the full version maximum total score is 30.

We are adding one additional measure that will be completed at every visit (baseline, 3 month, 6 month, 9 month, 12 month). Because our study is looking at social connectedness, which is affected by the pandemic, we are adding a new measure on the pandemic's effect that was just published (Cawton et. Al., 2020).

We are adding an additional measure (Older Adult Social-Evaluative Scale) that will be completed at Baseline and 12 months to assess factors that may affect non-compliance with intervention.

Inclusion/Exclusion criteria: Subjects must have access to a device and internet to complete remote study visits. Those who do not have access to a device/internet will be excluded at this time. For subjects who cannot use zoom and will do the MOCA without the visual elements, we will use a cutoff score of 15. A score of less than 15 will be used as exclusion for the telephone administered MoCA. This cutoff score is equivalent to our cutoff score for the full MOCA based on validation studies comparing the MoCA delivered in person with visual elements to the MoCA delivered via telephone without the visual elements (Zietemann et al., 2017).

Number of Subjects: The study will recruit and enroll up to 400 subjects into the study. The target number of randomized subjects is n=150 in each group. Due to greater than 10% of those enrolled being not eligible or not willing to be randomized, we must enroll up to 400 subjects to try to reach our target number of randomized subjects.

Recruitment procedures:

Strategy 2: We are including in this strategy a media press release and essay submission to newspaper to reach more potential subjects.

Strategy 9: We are adding a new strategy to use direct mailing. Sending informational postcards through the 'Every Door Direct Mail® (EDDM®)' program, which is a program created by the United States Postal Service®. The program enables advertisers to reach every address within targeted carrier routes, at reduced rates, without the need for additional mailing services or specific lists. We propose to use Staples Direct Mail because it is a service that combines printing and mailing for the EDDM process. The study team, therefore, will not have access to any names or addresses. This recruitment method allows demographic targeting, including by age. Without seeing individual household information, we are able to identify which mail carrier routes contain the highest density of adults age 65 and older. However, postcards are sent to every address/mailbox within your selected carrier routes. A carrier route is a group of addresses used by the USPS® to deliver mail in a specific area. ZIP Codes™ may contain anywhere from several to more than a dozen carrier routes depending on the rural or urban nature of the region. We can upload the informational postcard approved with this amendment to the Staples Direct Mail website, select which carrier routes we should like to use, and the rest is managed by Staples Direct Mail. We do not have access to the names/addresses of those sent mail. We propose to use a

Staples Direct Mail template; a graphic designer at Staples then uploads our approved text information into the template. Potential subjects can contact our study team and be screened using the contact information on the direct mailing.

Strategy 10: We are adding a new strategy to use recruitment e-mails sent to patients of Trillium Health who are age 60 and older. We have received approval from the Research Steering Committee at Trillium Health. An e-mail from Trillium Health with a short description of our study along with a link to our study website will be sent to any patient who is age 60 or older. The Research Steering Committee has approved the e-mail for this purpose. Our study staff will not have access to any Trillium patient information. Trillium staff will create and send the e-mails.

In addition to e-mails, recruitment letters from Trillium Health will be sent to patients of Trillium Health who are age 60 and older. We have received approval from the Research Steering Committee at Trillium Health. Letters will be generated and sent by staff at Trillium Health, and study staff will not have any access to any Trillium patient information. These letters, prepared by staff at Trillium Health, will introduce the study including a brochure. The letter will indicate it is sent by Trillium Health, and invite those who may be interested to call research staff. These letters will state that participation in the study is entirely voluntary, and that participation or non-participation will not influence one's medical care. Letters will only be sent to patients once.

In addition to the e-mails and letters, Trillium Health will also list our study on their research opportunities webpage. <https://www.trilliumhealth.org/patient-and-community-services/research-opportunities> A brief description of the study will be listed along with our contact phone number and e-mail address. An approved study recruitment flyer/brochure will also be included on the website.

We propose recruiting from Trillium Health to increase diversity and boost recruitment numbers. This is in support of an administrative supplement we previously received to increase recruitment of SGM (sexual and gender minority) older adults (supplement information submitted in modification #5: 4/12/19). E-mails will not be targeting any specific population and will be sent to all patients over age 60, however the Trillium population is an enriched sample regarding SGM because of who selects care at Trillium.

Strategy 11: We are adding recruitment strategies via our geriatric medicine practices at UR Medicine. The UR Medicine Geriatrics Group will place our informational brochures in waiting rooms and patient exam rooms. UR Medicine Home Care (URMHC) will share brochures with patients who receive their services. In addition we may contact potentially eligible URMHC clients who have indicated that they are interested in participating in research when they complete the consent process via URMHC. In 2021, URMHC developed and implemented a process for existing URMHC patients to indicate willingness to be contacted about participation in research studies. These procedures are part of a clinical workflow conducted by clinicians; responses are contained in a clinical database. Using this process, URMHC patients, while receiving HHC visits, will be asked if they agree to be contacted by URMC researchers for future research participation, knowing that each study will be introduced and consent will be sought individually. If the patient agrees to be contacted by URMC research about future

research opportunities, he/she will choose “yes”, sign, and indicate their preferred contact method (i.e., phone, email, or mail). This information has been incorporated electronically, along with the signature, in the URMHC electronic health records. Upon IRB approval, URMHC will provide a list of URMHC patients who have consented for future research contacts at the time for their initial HHC visits, along with their contact information. Study staff will contact those patients and explain the study per the verbal script. If interested, the screening questions will be completed by phone.

References

